#### Part 2 Cohort-expansion Phase:

Additional patients with AML or MDS with or without specific genetic mutations indicative of MAPK pathway activation will be recruited for treatment at the Recommended Phase 2 Dose (RP2D). Patients will receive twice daily oral doses of BVD-523 in 21-day treatment cycles until disease progression, unacceptable toxicity, or another withdrawal criterion is met. Treatment cycles will occur consecutively without interruption except when necessary to manage adverse events.

Total enrollment for Part 2 is targeted at approximately 40 patients. Patients will be enrolled into 1 of 2 treatment groups. Group assignments are made according to the following disease characteristics, which correspond to specific inclusion and exclusion criteria for Part 2:

- Group 1: patients with RAS mutant positive AML or MDS; n (evaluable)  $\leq 20$
- Group 2: patients with RAS mutant negative AML or MDS; n (evaluable)  $\leq 20$

#### Table 3.1Study Medication Dosing and Pharmacokinetics/Pharmacodynamics Chart

	Study Days			
	1	8± 1	15± 1	22± 1
BVD-523 dosing a	Х	Х	Х	Х
Pharmacokinetics	Х			Х
Pharmacodynamics	Х			Х

Dosing is twice daily in 21-day cycles until disease progression. Patients will take their study medication in the clinic on PK days. Patients may be treated beyond disease progression for additional 21-day cycles at the same or escalated dose level (see intra-patient dose escalation Sec 3.1.3) at the Investigator's discretion. Study medication for a week of dosing should be dispensed at each visit for treatment Cycles 1 and 2. For treatment cycles after Cycle 2, study medication will be dispensed to support the entire 3 week cycle.

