### 3.1.4.2 Definition of Dose Limiting Toxicity (DLT)

The DLT is defined using the Common Terminology Criteria for Adverse Events Version 4.0 (CTCAE v4.0) in the first 21 days of treatment. All toxicities will be considered related to BVD-523 if they cannot be definitively explained by underlying disease, intercurrent illness or concomitant medications.

- Any treatment emergent study drug related Grade 3 or Grade 4 non-hematologic toxicity unless clearly and incontrovertibly unrelated to BVD-523. Exceptions are Grade 3 or 4 nausea or vomiting that is controllable by anti-emetics or Grade 3 or 4 diarrhea controllable by optimal therapy such as loperamide. Grade 3 laboratory investigations other than serum creatinine, bilirubin, AST or ALT will not be considered a DLT unless they are associated with clinical manifestations.
- Study-drug related Grade 4 thrombocytopenia that was not present at study entry and that does not resolve within 7 days, unless clearly and incontrovertibly unrelated to BVD-523.
- Febrile neutropenia or Grade 4 neutropenia that was not present at study entry and that does not resolve within 7 days, unless clearly and incontrovertibly unrelated to BVD-523.
- Prolonged myelosuppression or pancytopenia with a hypocellular bone marrow and no marrow blasts lasting for 6 weeks or more that is not related to disease progression.

• Any study drug related toxicity that results in treatment delays of > 4 days, except when patient is experiencing rash in which case, patient may be off drug for up to 7 days while receiving treatment.

All subjects who are not evaluable for toxicity in Cycle 1 due to unrelated AEs will be replaced.

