### 5.2.4 Visit 4 (Day 15 ± 1)

The following procedures will be performed at Visit 4 (Day 15):

- Review medical history.
- Record medications including start/stop dates, indication, dose and frequency taken after Visit 3.
- Perform and record targeted physical examination as appropriate.
- Assess and record performance status (ECOG).
- Record vital signs (body temperature, systolic / diastolic BP and pulse rate).
- Collect blood samples for blood chemistries, hematology and creatinine clearance.
- Collect urine samples for urinalysis.
- Dispense drug supply for self-dosing.
- Obtain all unused study drug from patient.
- Assess study drug compliance by pill count.
- Assess and record AEs.

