### 5.2.5 Visit 5 (Day 22 ± 1 of Cycle 1, first day of Cycle 2)

The following procedures will be performed at Visit 5 (Day 22 of Cycle 1, Day 1 of Cycle 2):

- Review medical history including all cancer treatments received since previous visit.
- Record medications including start/stop dates, indication, dose and frequency taken after Visit 4.
- Perform and record targeted physical examination as appropriate.
- Measure and record weight in kg.
- Assess and record performance status (ECOG).
- Bone marrow aspirate and/or biopsy. Peripheral, Geimsa and Iron stained slides will be collected with each bone marrow aspirate or biopsy. Following Cycles 1 and 2, Day 22 bone marrow aspirates will be collected only every other cycle, i.e., Cycle 4, etc.
- Bone marrow cytogenetics in accordance with local pathology requirements. (Cytogenetics would preferably include at least 20 clones).
- Record vital signs. Measure body temperature, systolic / diastolic BP and pulse rate.
- Collect pre-dose blood samples for pharmacokinetic (PK), pharmacodynamic (PD), and PBMC analyses.
  - These assessments should be collected when the patient reaches steady state. Steady state refers to patients who have received at least 5 days, or 10 consecutive doses, of investigational product. If patients are not at steady state, these assessments will be rescheduled and completed at the next visit in which steady state is achieved.
- Collect blood samples for blood chemistries, hematology and creatinine clearance.
- Collect urine samples for urinalysis.
- Perform urine pregnancy test for female patients who are not postmenopausal or surgically sterile. If urine test is positive, collect blood for a serum pregnancy test. If
serum pregnancy test is positive, withdraw patient from study and contact Medical Monitor.

- Administer BVD-523 and dispense drug supply for self-dosing for Cycle, if appropriate, and remind patient of dosing instructions.
- Collect post-dose blood samples for pharmacokinetic (PK), pharmacodynamic (PD), and PBMC analyses.
  - These assessments should be collected when the patient reaches steady state. Steady state refers to patients who have received at least 5 days, or 10 consecutive doses, of investigational product. If patients are not at steady state, these assessments will be rescheduled and completed at the next visit in which steady state is achieved.
- Assess and record disease status (every 2 cycles).
- Obtain all unused study drug from patient.

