#### 5.4.1 Cycle 3 and Subsequent Cycles Visit (Day 1 ± 1 of each cycle)

The following procedures will be performed at Cycle 3 and Subsequent Cycles Visit:

- Review medical history
- Record medications including start/stop dates, indication, dose and frequency taken since previous visit.
- Perform and record targeted physical examination as appropriate.
- Assess and record performance status (ECOG).
- Measure weight in kg.
- Record vital signs. Measure body temperature, systolic / diastolic BP and pulse rate.
- Perform ECG if appropriate (Patients with a normal ECG during Cycle 1 need not have repeat ECGs during subsequent cycles).
- Collect blood samples for blood chemistries, hematology and creatinine clearance.
- Collect urine samples for urinalysis.
- Perform urine pregnancy test for female patients who are not postmenopausal or surgically sterile. If urine test positive, test, collect blood for a serum pregnancy test.
- Assess and record disease status (every 2 cycles).
- Assess and record AEs.
- Obtain all unused study drug from patient.
- Assess study drug compliance by reviewing pill count.
- Bone marrow aspirate and/or biopsy. Peripheral, Geimsa and Iron stained slides will be collected with each bone marrow aspirate or biopsy. Following Cycles 1 and 2, Day 22 bone marrow aspirates will be collected only every other cycle, i.e., Cycles 4, 6, etc.

- Bone marrow cytogenetics in accordance with local pathology requirements. (Cytogenetics would preferably include at least 20 clones).
- Dispense BVD-523 for 21 days ±4 days of Cycle. Extra doses may be dispensed at the Investigator's discretion to insure continuous dosing.

# 5.5 DESCRIPTION OF STUDY VISITS FOR PART 2

Study procedures for Part 2 will be the same as those for Part 1. If clinical experience gained in Part 1 requires significant deviations in Part 2 from the procedures in Part 1, these changes will be addressed in a protocol amendment.

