## 8.1.2 Dosing Information

BVD-523 is to be taken twice daily orally with at least 8 ounces of water for 21 days, at 12-hour  $\pm$  2 hour intervals. The study medication should be taken at the same time each day on an empty stomach, i.e., fasting (30-60 minutes before food or 2 hours after food). A patient that is observed to vomit an intact capsule after dosing in the clinic during the PK measurements may receive a substitute dose of drug. However, patients should be instructed NOT to take a substitute capsule if vomiting occurs after self-dosing at home. Missed doses should be skipped and not taken as a double dose at the next dosing timepoint.

Since this is a second-in-human study relatively little human toxicity has thus far been experienced. Therefore, dose modifications for any toxicity seen will be developed as data are accrued. However, patients experiencing DLT or unacceptable toxicity will have their treatment interrupted until the toxicity returns to  $\leq$  Grade 1 or pre-treatment baseline. BVD-523 treatment may then be re-initiated at the next lower dose level where the safety profile has previously been established, or between the dose level yielding unacceptable toxicity and the previous dose level, aligning with capsule dose availability. Such dose adjustments will be done in consultation with the Investigators and Medical Monitor of the study.

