7 DATA HANDLING METHODS

### 7.1 VISIT WINDOWS

All study data will be presented at the nominal visit obtained from the eCRFs, if available. Study day is defined as (date of visit – date of treatment initiation + 1). That is, study day 1 indicates the date of treatment initiation. In the case of early termination visit, the date of the visit will be used to calculate the nominal visit for the analysis.

If there are two or more assessments within a nominal visit, then the assessment that is closest to the scheduled time point/target day will be used in the analysis. If there is more than one closest value, then the evaluation occurring after the target day and prior to the date of last dose will be used in the analysis.

All values will be included in the data listings.

Study visit periods will be windowed as applicable according to the following:

Visit	Nominal Study Day	Study Day Window
Screening		-28 to -1
Baseline	1	N/A
(pre-dose and post-single dose)		(Other visits are scheduled based on this visit)
Cycle 1		
Day 8	8	7 to 9
Day 15	15	14 to 16
Cycle 2		
Day 1	22	21 to 23
Day 8	29	28 to 30
Day 15	36	35 to 37
Cycles 3-X		
Day 1	21*X + 1	-1 to +1

Values will be presented for all scheduled study visits according to the nominal visit obtained from the CRF. If an unscheduled visit falls in a visit window with an existing nominal visit assessment, the nominal assessment will be used for summary presentation. If no nominal visit assessment exists for a visit window with unscheduled visit(s), then the latest unscheduled visit

within the visit window will be used. If multiple nominal assessments are collected within the

same visit, the latest value and corresponding date will be used for summary presentation.

All values will be included in the data listings.

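### In Cycles 1 and 2 a week of drug per visit does not cover the 8- and 9-day gaps that the visit windows allow, so patients with in-window visits can run out

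*Protocol*

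**What the plan says.** - **Quantity.** The footnote to Protocol Table 3.1 reads "Study medication for a week of dosing should be dispensed at each visit for treatment Cycles 1 and 2". Footnote a to SAP Table 3.3 repeats it. Section 8.1.2 sets twice-daily dosing: "BVD-523 is to be taken twice daily orally with at least 8 ounces of water for 21 days".
- **Return.** Sections 5.2.3, 5.2.4 and 5.2.5 (Visits 3, 4 and 5) each include the step "Obtain all unused study drug from patient".
- **Windows.** Visit 2 is Day 1 with no tolerance. Visits 3, 4 and 5 are Days 8, 15 and 22, each ±1. Section 5.2.5 is headed "Visit 5 (Day 22 ± 1 of Cycle 1, first day of Cycle 2". SAP Section 7.1 uses the same windows and anchors them to the baseline visit, not to the preceding visit: "Other visits are scheduled based on this visit".
- **Continuity.** Section 3.1.2 calls for consecutive cycles, with adverse events as the only ground for interruption.
- **Later cycles.** Section 5.4.1, for Cycle 3 onward, says "Dispense BVD-523 for 21 days ±4 days of Cycle" and lets the investigator add doses so that dosing stays continuous. Cycles 1 and 2 have no such allowance.
- **Cycle 2 supply.** At Visit 5, Section 5.2.5 speaks of drug for the cycle, which does not match weekly dispensing.

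**The concern.** Seven days of drug matches the nominal visit spacing exactly and leaves no margin. The windows permit longer spacing, and the return step stops a patient from building a reserve after a short interval. The plan can therefore produce drug-free days with no deviation by patient or site.

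These days fall where they matter most. Dose-limiting toxicities (DLTs) are counted "in the first 21 days of treatment", and escalation rests on Cycle 1. Visit 5 supplies the steady-state half of the PK profile, which is a primary objective, and no routine PK sampling follows it. Missed doses before Day 22 mean that the exposure behind the escalation decision is below the assigned dose. A gap just before Visit 5 means that a profile labelled steady state may not be one.

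**Working it through.** **Inputs.** Supply is 7 days (14 doses) per visit, with nothing carried over. Visit 2 is on Day 1, Visit 3 on Days 7 to 9, Visit 4 on Days 14 to 16, and Visit 5 on Days 21 to 23. I assume that each supply starts on the day it is dispensed.

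**Formula.** Days without drug in an interval = max(0, gap − 7).

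**The plan's own case.** Visits on Days 1, 8, 15 and 22 give gaps of 7, 7 and 7 days and a shortfall of 0. The weekly supply is exactly enough.

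**In-window extremes.**

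| Interval | Shortest gap | Longest gap | Largest shortfall |
|---|---|---|---|
| Visit 2 to 3 | 7 − 1 = 6 | 9 − 1 = 8 | 1 day (2 doses) |
| Visit 3 to 4 | 14 − 9 = 5 | 16 − 7 = 9 | 2 days (4 doses) |
| Visit 4 to 5 | 21 − 16 = 5 | 23 − 14 = 9 | 2 days (4 doses) |

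**Days 1 to 21.** There are 3 × 3 × 3 = 27 combinations of Visits 3, 4 and 5. Only five have no drug-free day in Days 1 to 21: (7, 14, 21), (8, 14, 21), (8, 15, 21), (8, 15, 22) and (8, 15, 23). The other 22 have at least one. The maximum is 2 days: 4 of 42 doses = 9.5%. It occurs in five combinations: (7, 16, any Visit 5), (9, 14, 22) and (9, 14, 23). The remaining 17 lose one day, 2 of 42 doses = 4.8%.

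**Just before the Visit 5 PK.** The gap exceeds 7 days when Visits 4 and 5 fall on (14, 22), (14, 23) or (15, 23). With three possible days for Visit 3 this is 9 of 27. The full 2-day gap, (14, 23), is 3 of 27.

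**Probabilities.** The documents give no distribution of visit days, so these rest on an assumption: visits independent, with p on the exact day and q on each side.

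- P(loss in Days 1 to 21) = 1 − (q³ + pq² + p²), which collects the five combinations above.
- P(out of drug before Visit 5) = 2pq + q².

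| Assumption | Loss in Days 1 to 21 | Out of drug before Visit 5 |
|---|---|---|
| p = 0.80, q = 0.10 | 1 − (0.001 + 0.008 + 0.640) = 35% | 0.160 + 0.010 = 17% |
| p = 0.90, q = 0.05 | 1 − (0.0001 + 0.0023 + 0.8100) = 19% | 0.0900 + 0.0025 = 9% |
| Uniform in window | 22/27 = 81% | 9/27 = 33% |

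Two-day losses within Days 1 to 21 are uncommon if most visits are on time. At p = 0.80 the chance is q² + q²(1 − q) = 0.010 + 0.009 = 1.9%.

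**Does the return step drive this?** Only in part. If patients kept leftover drug, 19 of the 27 combinations would still run short before Visit 5, by at most 1 day. With 9 days of supply per visit, none would.

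**The case against.** **The PK rule already handles gaps.** Sections 5.2.5 and 6.9.1 reschedule sampling if the patient is not at steady state on Day 22. This is a real safeguard, but a partial one. Steady state is defined as having received 5 days or 10 consecutive doses, without saying that they must come immediately before sampling. Read literally, a patient who took 14 doses and then ran out still qualifies.

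**The quantity may be settled elsewhere.** Section 8.1.1 refers dispensing to Pharmacy Instructions in the study manual, which is not available here. The footnote says only what should be dispensed, and Section 5.2.7 allows unscheduled visits, at which a site could resupply. This stands: the documents show that patients can run out, not that they do. It does not remove the conflict, because the footnote states a quantity that the windows outrun.

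**The loss is small.** This also stands. It is at most 2 of 21 days, and usually one day when it happens.

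Four stronger readings are tempting, and the documents do not support them:

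- *Three days, or 6 of 42 doses (14%), lost in Cycle 1.* Visits on Days 9, 14 and 23 do miss Days 8, 21 and 22, but Day 22 lies outside both the 21-day DLT window and the 42-dose denominator.
- *The Day 22 profile starts from almost no drug.* The only half-life given, 2 to 4 hours in Section 1.5.3, is animal data. No human value is stated.
- *The maximum tolerated dose (MTD) is pushed upward.* Lower exposure points that way, but nothing in the documents gives the effect of one or two missed days on DLT incidence.
- *Pill-count compliance is reduced.* Neither Protocol Section 8.3 nor SAP Section 10.1 defines the denominator. A patient who takes all 14 doses dispensed is fully compliant against that count.

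**Conclusion.** The conflict is real and modest. In Cycles 1 and 2 the stated weekly supply, the return of unused drug and the visit windows cannot all hold together with uninterrupted dosing. In-window visits can leave a patient without drug for 1 day (first interval) or up to 2 days (each later interval), with a maximum of 2 days within Days 1 to 21. Visits exactly on schedule cause no shortage.

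The counts (22 and 9 of 27) follow from the documents, given that each supply starts on the day it is dispensed. The percentages (35% and 17%, or 19% and 9%) depend on assumed visit timing. If the Day 1 clinic dose came from separate stock, which is not stated, an 8-day first gap would be one dose short instead of two.

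For DLTs, the effect is toward lower exposure, of unknown size. For PK, the risk is an occasional Visit 5 profile that meets the written definition of steady state after a supply gap. The Cycle 1 result does not depend on how the Cycle 2 wording is resolved.

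**What to change.** Reconcile the footnotes to Protocol Table 3.1 and SAP Table 3.3 with four things: the visit windows (Protocol Sections 5.2.3 to 5.2.5, SAP Section 7.1), the return-of-drug steps, the Visit 5 wording on supply for the cycle, and the allowance in Section 5.4.1. The supply dispensed at each Cycle 1 and Cycle 2 visit should cover the longest gap the windows permit, and the study manual should be checked for the same quantity. Dose and dosing schedule are unchanged.

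The cost is one footnote in each document, the matching wording at Visit 5, and a few more capsules per dispensing. Returned capsules are already collected and counted.

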## 3.1.3 Summary of Dose Escalation

#### Table 3.2Summary of Dose Escalation

Observed Safety Outcomes	Action
1 DLT in 3 patients	Expand cohort up to 6 patients
1 DLT in 6 patients	Escalate by $\leq 50\%$ to next dose level
> 1 DLT in $\leq$ 6 patients	Stop dose escalation

*Note*: DLT is defined in detail in Section 3.1.4.2 below.

Each cohort can only begin when the previous cohort has completed treatment to at least the end of Cycle 1 without fulfilling a criterion which would prevent dose escalation. Intra-patient dose escalation will be permitted with consensus among the Principal Investigator, Medical Monitor, and Sponsor, to a dose not to exceed that for which 21 days of treatment has been deemed safe.

Although dose escalation decisions will be taken upon review of the data from Cycle 1, safety data will also be collected from all patients continuing treatment and these data will be reviewed periodically by the Safety Monitoring Committee. Any detected cumulative toxicity may require later dose reductions or other action as appropriate, including having an effect on the RP2D.

### 3.1.4 Definition of MTD, DLT, and RP2D

#### 3.1.4.1 Definition of Maximum Tolerated Dose (MTD)

MTD is defined as the highest dose cohort at which < 33% of patients experience BVD-523 related DLTs in the first 21 days of treatment.

### 3.1.4.2 Definition of Dose Limiting Toxicity (DLT)

The DLT is defined using the Common Terminology Criteria for Adverse Events Version 4.0 (CTCAE v4.0) in the first 21 days of treatment. All toxicities will be considered related to BVD-523 if they cannot be definitively explained by underlying disease, intercurrent illness or concomitant medications.

- Any treatment emergent study drug related Grade 3 or Grade 4 non-hematologic toxicity unless clearly and incontrovertibly unrelated to BVD-523. Exceptions are Grade 3 or 4 nausea or vomiting that is controllable by anti-emetics or Grade 3 or 4 diarrhea controllable by optimal therapy such as loperamide. Grade 3 laboratory investigations other than serum creatinine, bilirubin, AST or ALT will not be considered a DLT unless they are associated with clinical manifestations.
- Study-drug related Grade 4 thrombocytopenia that was not present at study entry and that does not resolve within 7 days, unless clearly and incontrovertibly unrelated to BVD-523.
- Febrile neutropenia or Grade 4 neutropenia that was not present at study entry and that does not resolve within 7 days, unless clearly and incontrovertibly unrelated to BVD-523.
- Prolonged myelosuppression or pancytopenia with a hypocellular bone marrow and no marrow blasts lasting for 6 weeks or more that is not related to disease progression.

• Any study drug related toxicity that results in treatment delays of > 4 days, except when patient is experiencing rash in which case, patient may be off drug for up to 7 days while receiving treatment.

All subjects who are not evaluable for toxicity in Cycle 1 due to unrelated AEs will be replaced.

